3.1.3 Follow-Up Phase

Following the remission induction phase, patients will be followed for a minimum of 12 months with visits every 3 months, in accordance with the schedule of assessments (see [Appendix 1](#)). The optimal treatment after rituximab induction for GPA or MPA has

not been established in adults or in pediatric patients. After Month 6, patients who are protocol remission failures or experience disease flare that cannot be controlled by glucocorticoids alone should receive treatment in accordance with local standard of care at the discretion of the investigator and will remain in the study (see Section 4.4.2.1).

After Month 6, if patients require retreatment with rituximab, additional courses will be provided by the Sponsor until the common closeout date. Retreatment with rituximab is at the discretion of the investigator and may be considered based on disease activity, previous response to treatment, and the investigator's assessment of the risks with rituximab.

After Month 18, patients will be followed at study visits every 3 months until the common closeout date. The procedures performed at the follow-up visits will be similar to those performed at the Month 18 visit. After the common closeout date, patients whose B cells remain depleted and/or who have immunoglobulin levels below the lower limit of normal (LLN) for the population will enter extended follow up.

The schedule of assessments is provided in [Appendix 1](#).

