4.3.4 Retreatment with Rituximab

After Month 6, if patients require retreatment with rituximab, further courses will be provided by the Sponsor until the common closeout date. The dose of rituximab and the frequency of retreatment for the maintenance of remission will be at the discretion of the investigator.

Following administration of the first infusion the investigator should review the following safety criteria before administering subsequent infusions of rituximab.

The following are absolute contraindications to receipt of further infusions of rituximab in this study:

- An infusion reaction which necessitated complete discontinuation of the study infusions
- Significant deterioration in patient's general health status since inclusion into the study that results in the patient meeting the exclusion criteria related to General Health
- Emergent primary or secondary immunodeficiency recognized during the study period, including new HIV infection, de novo hepatitis B, hepatitis C, or active tuberculosis infection

Patients who have any of the absolute contraindications to receipt of study infusions with rituximab will be withdrawn from the study and should be encouraged to enter Follow Up.

Patients who develop malignancy during the study will not be able to receive further courses of treatment with the study medication. However, patients with basal cell carcinoma, squamous cell carcinoma of the skin or melanoma in situ (Clarke's Level I), or cervical carcinoma in situ with no stromal invasion (stage 0), which have been completely excised and can be considered as cured, may be retreated with study medication at the discretion of the investigator.

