5.2.3.3 Infections

Given the mechanism of action of rituximab and the knowledge that B cells play an important role in maintaining normal immune response, patients may have an increased risk of infection following rituximab therapy. Rituximab should not be administered to patients with an active infection or to severely immunocompromised patients (e.g., those in whom levels of CD4 or CD8 are very low). Physicians should exercise caution when considering the use of rituximab in patients with a history of recurring or chronic infections or with underlying conditions that may further predispose patients to serious infection. Patients who develop infection following rituximab therapy should be promptly evaluated and treated appropriately. If a patient experiences a new infection during the intervening time between any of the four rituximab infusions, the subsequent infusion should be delayed (up to a maximum of 14 days) until the infection has completely resolved and treatment with any anti-infective medications has been completed. Receipt of further rituximab infusions is at the discretion of the investigator. Remaining infusions should be scheduled so that they are given 1 week apart.

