2. STUDY DESIGN

This is a Phase IIa, international, multicenter, open-label, single-arm study. The primary objectives are to evaluate the safety and tolerability and the PK parameters of rituximab in pediatric patients with severe GPA or MPA.

The study comprises an initial 6-month remission induction phase; rituximab is administered on Days 1, 8, 15 and 22 during this phase. The remission induction phase is followed by a minimum 12-month follow-up phase, after which patients are followed up 3-monthly until the common closeout date, which occurs when the final participant enrolled has completed his or her Month 18 study visit (see [Appendix 2](#)).

Following the remission induction phase (month 6), if required for the maintenance of remission, further courses of rituximab may be given, with the dose and the frequency of retreatment at the discretion of the investigator.

At the common closeout date, patients whose B cells remain depleted and/or have immunoglobulin levels below the LLN for the population, continue to attend study visits every 3 months until their B-cell counts have returned to baseline level or to within the normal range for the population, whichever is lower, and until their immunoglobulin levels have returned to within normal limits for the population. Patients that receive any B-cell therapy or other agent that affects the return of B-cells including but not limited to rituximab, CYC, AZA, on or after the common closeout date, he or she will not be followed any further.

The Study Schema is given in [Appendix 1](#) and the Schedule of Assessments is given in [Appendix 2](#).

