
ID: EX001SP
 
Rituximab Treatment Exposure by visit during Remission Induction Phase
	
STREAM Template: None
 
Analysis Population: Safety Evaluable Population
 
Analysis Variables: Number of infusions started, Number infusions completed without them being interrupted/modified, Number of patients with interrupted/modified infusions by infusion number, total dose of RTX. The number of infusions categories need to run from 1 (0 for number completed if necessary) to the maximum number of infusions started.
 
Analysis visits to include are: Baseline, Weeks 1 to 3, Months 1, 2, 4, 6
 
Statistics and Calculation Methods: The Infusion Interrupted/Modified rows count the number of Yes's from the "Was the infusion interrupted/modified" question and the denominator for the %s will be the number of patients who started that infusion number and so will correspond to the appropriate row from "Number of infusions started".
 
Percentages are based on:
 
 1. for "Infusion started" section: based on n 2. for "Infusion Interrupted/Modified" section: based on nn*, where nn* is the number of infusions in corresponding visit.
---	---

```

Rituximab
(N=nn)
-----
Infusions started
n                               nn
Baseline                       nn* (xx.x%)
Week 1                         nn* (xx.x%)
Week 2                         nn* (xx.x%)
Week 3                         nn* (xx.x%)
Month 1                        nn* (xx.x%)
...

Infusion Interrupted/Modified
n                               nn
Baseline                       nn/nn* (xx.x%)
Week 1                         nn/nn* (xx.x%)
Week 2                         nn/nn* (xx.x%)
Week 3                         nn/nn* (xx.x%)
Month 1                        nn/nn* (xx.x%)
...

Total number of infusions completed
n                               nn
0                               nn (xx.x%)
1                               nn (xx.x%)
2                               nn (xx.x%)
...

Total cumulative dose (mg)
n                               nn
Mean (SD)                      xxx.x (xx.x)
Median                          xx.x
Q1 - Q3 (IQR)                  xx.x- xx.x (xx.x)
Min - Max                       xx - xxx

```

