
ID: EX001.1SP
 
Summary of Rituximab Exposure
	
STREAM Template: None
 
Analysis Population: Safety Evaluable Population
 
Analysis Variables: See mock. Percentages are based on n. Include data from Day 1 to common closeout date.
 
- study end date =
 
 1. For early discontinuation or completion patients: minimum of or early withdrawal/discontinuation or patient completed study 2. For the rest of patients: minimum of common closeout date and last known alive date 
Duration of observation = study end date – study start date + 1.
 
Date of last contact is the last available date of efficacy, complete medication start date, laboratory, adverse event assessments, early withdrawal visit, date of last contact or date of death.

---	---

Total number of Infusions administered	
n	nn
Mean (SD)	xxx.x (xx.x)
Median	xx.x
Q1-Q3 (IQR)	xx.x-xx.x (xx.x)
Min - Max	xx - xxx
Total cumulative dose (mg)	
n	nn
Mean (SD)	xxx.x (xx.x)
Median	xx.x
Q1-Q3 (IQR)	xx.x-xx.x (xx.x)
Min - Max	xx - xxx
Duration of Observation (Months)	
n	nn
Mean (SD)	xx.x (xx.x)
Median	xx.x
Q1-Q3 (IQR)	xx.x-xx.x (xx.x)
Min - Max	xx.x - xx.x
Duration of Observation (Months)	
n	nn
Duration ≤ 6	nn (xx.x%)
6 < Duration ≤ 12	nn (xx.x%)
12 < Duration ≤ 18	nn (xx.x%)
18 < Duration ≤ 24	nn (xx.x%)
24 < Duration ≤ 36	nn (xx.x%)
36 < Duration ≤ 48	nn (xx.x%)
48 < Duration ≤ 60	nn (xx.x%)
Duration > 60	nn (xx.x%)
Total patient years of observation	xxx.xx

ID: EX001.2SP

STREAM Template: None

Rituximab
Administration over
Course of study

[figure not shown]
Analysis Population: Safety Evaluable Population

Plot of:

Y-Axis: Patient ID

X-Axis: Study Visit

See mockup.

ID: EX002SP

Listing of Rituximab Administrations, Interruptions and Modifications

STREAM Template: None

Analysis Population: Safety Evaluable Population

Column Variables: Include data from Day 1 to common closout date.

Add "Dose Administered" column in "mg/m²" calculating as follows:

administered dose (mg/m²) = dose administered (mg) / BSA (m²),

where

$$BSA = \text{body surface area} = \text{sqrt} [BW \times Ht / 3600]$$

BW = weight (kg)

Ht = height (cm)

See mockup

Sorting: Sort by center / patient ID and treatment administration day.

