
ID: AE002.2SP
 
Summary of Infusion Related Reactions (IRRs) by Visit
	
STREAM Template: DMT01
 
Analysis Population: Safety Evaluable Population
 
Analysis Variables: See mockup.
 
Column Variables: Infusion numbers.
 
Statistics and Calculation Methods: Include two tables in one output file:
 
 1. For remission induction phase. 2. For overall period, Day 1 to common closeout date. 
Infusion Related Reactions (IRRs) are defined as:
 
 • events that occur during or within 24 hours of an infusion and fall within Roche standard AEGT Infusion Related Reactions + Hypersensitivity 
Count multiple symptoms as one IRR for each infusion.
 
Percentages are based on n.
 
Visits to be included: Baseline, Week 1 to 3, month 6, 12 and 18.
 
Symptom of IRR = Reported term.
 
Numeric Precision and Formatting of Statistics: See mockup

--	--

Preferred Term/ Symptom of IRR	Rituximab (N=57)				
	Infusion 1 ...	Infusion 4	Infusion 5	Infusion 8	Infusion 10
Number of patients who had an infusion (n)	57	56	56	54	54
Infusion related reaction*					
Total No. of patients with events	5 (8.8%)	1 (1.8%)	2 (3.6%)	1 (1.9%)	0
bronchospasm	1 (1.8%)	0	0	0	0
cough	1 (1.8%)	0	0	0	0
exanthema	0	0	0	1 (1.9%)	0
metallic taste, tingling at the back of the throat	0	1 (1.8%)	0	0	0
pruritus	1 (1.8%)	0	0	0	0
skin rash	1 (1.8%)	0	0	0	0
tightness in the throat	0	0	1 (1.8%)	0	0
tingling at the back of the throat during the	0	0	1 (1.8%)	0	0

ID: AE004SP to ID: AE020SP
 
Adverse Event Subsets during Remission Induction Phase and Overall
	
STREAM Template: AET02
 
Analysis Population: Safety Evaluable Population
 
Subset: Same table contents and format, except use the following subsets (see also the beginning of this section):
																										

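### AE002.2SP, the per-infusion IRR table, contradicts itself: it is to run to common closeout, but its visit line would drop retreatment infusions given away from Months 6, 12 and 18

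*SAP*

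**What the plan says.** AE002.2SP (SAP Section 6) asks for two tables in one file: one for the remission induction phase and one described as "For overall period, Day 1 to common closeout date". The columns are infusion numbers, several symptoms at one infusion count as one IRR, and each column has its own n, the number of patients who had that infusion. The specification then adds "Visits to be included: Baseline, Week 1 to 3, month 6, 12 and 18".

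Retreatment is not tied to visits. Protocol 4.3.4 says "The dose of rituximab and the frequency of retreatment for the maintenance of remission will be at the discretion of the investigator", and Protocol 3.1.3 says "additional courses will be provided by the Sponsor until the common closeout date". SAP Section 2 agrees: further courses may be given "with the dose and the frequency of retreatment at the discretion of the investigator".

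The exposure outputs handle the same period differently. EX001.1SP (SAP 5.1) says "Include data from Day 1 to common closeout date" and has observation categories running beyond 60 months. EX002SP lists each infusion over that period.

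**The concern.** The period, the columns and the denominator call for every infusion; the visit line calls for a selection. A programmer who follows the visit line produces a table headed as overall that describes only some retreatment infusions, and whose n is no longer the number of patients who had that infusion.

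Adverse event frequency, nature and severity is a primary outcome, and this is the table that would show whether reactions recur on retreatment. The other visible outputs do not replace it:

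- AE001SP has one row counting patients with at least one IRR. A child who reacts in induction and again on retreatment adds nothing further to its overall row.
- The subset list AE004SP to AE020SP has no IRR entry, and AE018SP covers events other than IRRs.
- Protocol 5.3.5.1 has events within 24 hours of an infusion recorded as separate signs and symptoms, so the general tables contain them without identifying them as IRRs.

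Induction rates cannot simply be carried over to retreatment. Induction follows at least three IV methylprednisolone doses, which Protocol 5.2.3.1 says may help prevent severe reactions; Protocol 4.3.4 requires no such doses before retreatment.

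**Working it through.** The plan gives no figure to reproduce. The check is how much of the retreatment period the listed visits cover, and what that implies for infusions.

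**Inputs.** SAP 3.3, Table 1: Month 6 is Days 165–210, Month 12 is Days 335–395 and Month 18 is Days 500–590. Assessments outside the windows are listed but not used in by-time-point summaries. Retreatment is taken to start after Day 180.

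**Calendar days covered, from Day 181**

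- Month 6: 210 − 181 + 1 = 30
- Month 12: 395 − 335 + 1 = 61
- Month 18: 590 − 500 + 1 = 91
- Total: 30 + 61 + 91 = 182
- Days 181 to 590: 590 − 180 = 410, so 182/410 = 44.4% covered and 228 days (55.6%) not covered
- After Day 590: no days covered

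For longer follow-up (end dates assumed), the numerator stays at 182:

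- To Day 730 (Month 24): 182/550 = 33.1%
- To Day 1096 (Month 36): 182/916 = 19.9%
- To Day 1826 (Month 60): 182/1646 = 11.1%

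With the narrower windows of Protocol Appendix 2 (±5 days at Month 6, ±10 at Months 12 and 18), coverage over Days 181 to 590 is 5 + 21 + 21 = 47, and 47/410 = 11.5%.

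**From days to infusions.** The documents give no retreatment dates, so the loss depends on the assumed schedule. With one infusion per course, given at planned visits:

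- Every six months from Month 6: Months 6, 12 and 18 are all listed, so 0 of 3 are lost by Month 18. Months 24, 30 and 36 are not listed, so 3 of 6 are lost by Month 36.
- Every six months from Month 9: Months 9, 15, 21 and so on are never listed, so all are lost.

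For a course of four weekly infusions starting on any day from 181 to 590, 186 of 410 start days put no infusion in a listed window, 119 put all four in, and the remaining 105 split the course.

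**Induction part.** Protocol 5.2.3.3 says that after a new infection "the subsequent infusion should be delayed (up to a maximum of 14 days) until the infection has completely resolved", with the remaining infusions one week apart. If infusion 2 slips from Day 8 to Day 8 + 14 = 22, infusions 3 and 4 fall on Days 29 and 36. Table 1 assigns Days 26–44 to Month 1, which AE002.2SP does not list. EX001SP, the exposure table for the same phase, does: "Analysis visits to include are: Baseline, Weeks 1 to 3, Months 1, 2, 4, 6". This loss arises only if there is such a delay and Table 1 windows are also applied to numbered infusions.

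**The case against.** The strongest reply is that this is an ambiguity, not a certain loss. Three features of AE002.2SP point to every infusion and only one line points the other way. The mock-up shows N=57 while other shells in this SAP show N=25, so the visit line may have been carried over from another study. That stands as far as it goes: the loss is conditional on the line being applied. But the line is an explicit restriction, the table is titled as being by visit, and the mock-up columns skip infusion numbers, so applying it is a natural reading.

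A reader might also infer more than the documents support:

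- **That retreatment IRRs go unreported.** They do not. AE001SP's IRR row, the serious adverse event tables, the general and graded adverse event tables and the listings have no such visit limit. Section 6 also names IRRs among its summaries by study phase. Only the breakdown by infusion is at risk.
- **That more than half of retreatment infusions are lost.** The 55.6% is a share of days. Months 6, 12 and 18 are the SAP's key time points, and six-monthly dosing from Month 6 would match them.
- **That late serious reactions would be hidden.** In the adult rheumatoid arthritis data in Protocol 1.2.2, 18 − 10 = 8 of 18 serious IRRs came after Course 1. But AE002.2SP has no seriousness row, and serious IRRs reach the serious adverse event tables regardless. The same source gives 16 of 3194 patients with a serious IRR; at that rate 25 children would yield 25 × 16/3194 ≈ 0.13.
- **That the outputs would fail to reconcile because of this.** AE001SP counts patients, AE002.2SP counts by infusion and EX001.1SP summarises infusion numbers. They would not add up to one another even after the correction.

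**Conclusion.** Wrong as written; minor severity. AE002.2SP gives two instructions that conflict whenever an infusion falls outside the listed visits, and the protocol permits that at any time from after Month 6 to common closeout. If the visit line is followed, those infusions and their IRRs leave both numerator and n. Under Table 1 this includes every infusion after Day 590.

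The size in infusions cannot be stated from the documents: it ranges from none by Month 18 to all retreatment infusions across the schedules assumed above. The conclusion rests on the visit line being applied and on no redacted output giving IRRs by infusion. A loss of induction infusions is possible but needs two further conditions, so it is secondary. The study is single-arm and descriptive, and the primary safety outcome is otherwise reported, which keeps the severity low.

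**What to change.** In AE002.2SP, delete the visit list. Report all rituximab infusions from Day 1 to common closeout by infusion number, with n equal to the patients who started that infusion. Assign induction infusions 1 to 4 by number whatever their study day.

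This is a short SAP edit. It needs no protocol change and no new data, since EX002SP already lists infusions over the full period. The cost is that columns for late infusion numbers will hold few children and may need pooling, ideally under a rule set in advance. A split of first course against retreatment, and rows by grade or seriousness, would be useful but are optional.

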5.3.5.1 Diagnosis versus Signs and Symptoms

Infusion-Related Reactions

AEs that occur during or within 24 hours after study drug infusion should be captured as individual signs and symptoms rather than a diagnosis of allergic reaction or infusion reaction.

Other Adverse Events

For AEs other than IRRs, a diagnosis (if known) should be recorded on the Adverse Event eCRF rather than individual signs and symptoms (e.g., record only liver failure or hepatitis rather than jaundice, asterixis, and elevated transaminases). However, if a constellation of signs and/or symptoms cannot be medically characterized as a single diagnosis or syndrome at the time of reporting, each individual event should be recorded on the Adverse Event eCRF. If a diagnosis is subsequently established, all previously reported AEs based on signs and symptoms should be nullified and replaced by one AE report based on the single diagnosis, with a starting date that corresponds to the starting date of the first symptom of the eventual diagnosis.

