
ID: AE024SP
 
Common Adverse Events Reported in $\geq 10\%$ of Patients during Remission Induction Phase and Overall
	
STREAM Template: None
 
Analysis Population: Safety Evaluable Population
 
Analysis Variables:
 
Table of AEs grouped by System Organ Class (SOC) and listed by Preferred Term (PT) that occurred at a frequency $\geq 10\%$ for each phase.
 
Note: "with at least one AE " means "with at least one AE which occurred for $\geq 10\%$ of patients".
 
Numeric Precision and Formatting of Statistics: See mockup.

--	---

MedDRA System Organ Class	RITUXIMAB (N=25)
Total number of patients with at least one AE	24 (96.0%)
UPPER RESPIRATORY TRACT INFECTION	11 (44.0%)
HEADACHE	10 (40.0%)
DIARRHOEA	8 (32.0%)
EPISTAXIS	7 (28.0%)
ARTHRALGIA	6 (24.0%)
CHEST PAIN	5 (20.0%)
CONJUNCTIVITIS	5 (20.0%)
COUGH	5 (20.0%)
GRANULOMATOSIS WITH POLYANGIITIS	5 (20.0%)
NAUSEA	5 (20.0%)
PYREXIA	5 (20.0%)
HYPOGAMMAGLOBULINAEMIA	3 (12.0%)
MIGRAINE	3 (12.0%)
NASOPHARYNGITIS	3 (12.0%)
PHARYNGITIS	3 (12.0%)
RHINITIS	3 (12.0%)
TREMOR	3 (12.0%)
URINARY TRACT INFECTION	3 (12.0%)
VIRAL INFECTION	3 (12.0%)
VOMITING	3 (12.0%)

Investigator text for AEs is coded using MedDRA version 20.1.
Percentages are based on N.
Table includes only AEs occurring in $\geq 10\%$ of patients in at least one treatment group.
For frequency counts by preferred term, multiple occurrences of the same AE in an individual are counted only once.

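### The infusion-reaction table (AE002.2SP) labels symptom rows by the investigator's wording rather than the MedDRA preferred term, so symptom-level counts per infusion can be split

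*SAP*

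**What the plan says.** SAP section 6, output AE002.2SP, tabulates IRRs with one column per infusion. An event qualifies if it falls during an infusion or in the following 24 hours and belongs to the sponsor's standard grouping for infusion reactions and hypersensitivity. For the overall count the rule is "Count multiple symptoms as one IRR for each infusion". Percentages use the patients who had that infusion as denominator.

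For the symptom rows the rule is "Symptom of IRR = Reported term". The row header of the mock-up reads "Preferred Term/ Symptom of IRR", but the only grouping row shown is a single infusion-reaction heading, with free text below it. Two of those rows read "metallic taste, tingling at the back of the throat" and "tingling at the back of the throat during the".

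Two other places bear on this:

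- Protocol 5.3.5.1 says that events during or within 24 hours of an infusion "should be captured as individual signs and symptoms rather than a diagnosis of allergic reaction or infusion reaction".
- The footnote to the AE024SP mock-up in SAP section 6 says "Investigator text for AEs is coded using MedDRA version 20.1". AE002SP, the subset tables, AE021SP and AE024SP all count by preferred term, with a patient counted once per term.

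**The concern.** Under the protocol's recording rule, each symptom of an infusion reaction is a separate adverse event record with its own coded term. A layout with one infusion-reaction heading and verbatim symptoms beneath it would suit a trial that records the diagnosis and describes the symptoms in text. Here it sets aside coding that already exists and depends on how investigators at about 23 sites in eight countries (Protocol 3.1.1) word the same complaint.

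The nature and frequency of adverse events are a primary outcome (Protocol 3.4.1.1, SAP 2.1.1), and infusion reactions are an expected risk of the drug (Protocol 5.2.3.1). A reader who wants to know which symptoms occur at which infusion has only this table, and its symptom rows may be fragmented.

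**Working it through.** **1. Reproduce the mock-up.** Formula: patients with the event ÷ patients who had that infusion. The denominators shown are 57, 56, 56, 54 and 54 for infusions 1, 4, 5, 8 and 10.

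- Total rows: 5/57 = 8.8%, 1/56 = 1.8%, 2/56 = 3.6%, 1/54 = 1.9%.
- Single-patient symptom rows: 1/57 = 1.8%, 1/56 = 1.8%, 1/54 = 1.9%.

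All agree with the printed figures. The symptom rows shown at infusion 1 add to 4 against a total of 5, and the header has N=57 where this trial plans 25. The mock-up is therefore a shell, not data from this trial.

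**2. Merge the mock-up rows that name the same symptom.**

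- Throat tingling: row "metallic taste, tingling at the back of the throat" has 1 patient at infusion 4, and row "tingling at the back of the throat during the" has 1 at infusion 5. The merged row has 1/56 = 1.8% at infusion 4 and 1/56 = 1.8% at infusion 5.
- Rash and exanthema, if they share a preferred term (an assumption, since the coding dictionary is not in the documents): 1/57 = 1.8% at infusion 1 and 1/54 = 1.9% at infusion 8.

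No cell changes, because the duplicates fall at different infusions. The mock-up shows free-text rows, one of them combining two symptoms. It does not show an understated percentage.

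**3. When a percentage does change.** Take the planned 25 patients (SAP 2.2), all receiving the infusion. Let k of them have the same symptom at that infusion, each worded differently (an assumed worst case). Each verbatim row shows 1/25 = 4.0%. The preferred-term row shows k/25.

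| k | each verbatim row | preferred-term row |
|---|---|---|
| 2 | 4.0% | 8.0% |
| 3 | 4.0% | 12.0% |
| 4 | 4.0% | 16.0% |
| 5 | 4.0% | 20.0% |

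If all k use the same words, nothing is lost. The truth lies between these extremes, and the documents do not say where.

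**4. Can the reader add the rows?** No. Two rows of 1/25 could be two children (2/25 = 8.0%) or one child with a symptom entered twice in different words (1/25 = 4.0%). The table does not tell these apart.

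**5. What does not move.** The total row collapses symptoms to one IRR per infusion. Membership depends on the sponsor's event grouping, not on the row label. AE001SP counts patients with any IRR. None of these depends on wording.

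**6. Is the information elsewhere?** AE002SP, AE021SP and AE024SP give preferred terms, but for all events whatever their timing and not by infusion. AE018SP covers events other than IRRs. The itemised subset list goes from AE012SP to AE014SP, with no AE013SP. No itemised output gives IRR symptoms by preferred term and infusion.

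**The case against.** The strongest reply is that this is a display choice in one descriptive table of a 25-patient study without hypothesis tests. Verbatim text keeps detail that coding may lose, IRR incidence is protected, and each symptom still enters the general tables by preferred term. The mock-up is borrowed, as other shells in the SAP are, and its combined row would break the protocol's rule of one event term per field (Protocol 5.3.5), so it is weak evidence of how this trial's rows would look. The opening list of SAP section 6 names IRRs between opportunistic infections and cardiac events, where AE013SP would fall, so a preferred-term IRR table may have been intended.

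Much of this stands, and it limits the point. It does not remove it: the rule for the symptom rows is explicit, the general tables are neither restricted to IRRs nor split by infusion, and an unlisted output cannot be relied on.

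A reader might infer three stronger things that the documents do not support:

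- That IRR frequency is understated. It is not, for the reasons in step 5.
- That the mock-up demonstrates understated symptom frequencies, with two tingling rows differing only in wording. One row adds metallic taste, the other is cut off mid-phrase, and merging changes no cell.
- That the understatement is a particular multiple. Any such factor comes from an assumed split of wordings.

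Differences from the general tables are not in themselves an error either. Denominators and event scope differ, and would still differ after the change.

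**Conclusion.** The point holds at symptom level only. As written, AE002.2SP can split one symptom over several rows within an infusion, in the only itemised table that shows IRR symptoms by infusion. For two of 25 children with differently worded reports of the same symptom at the same infusion, the effect would be two rows of 4.0% in place of 8.0%. That example assumes all 25 receive the infusion and the two wordings code to one preferred term. The actual extent depends on the wordings received and cannot be derived from the documents. Overall IRR incidence per infusion and the AE001SP count are unaffected. Severity is low.

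**What to change.** In AE002.2SP:

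- define the symptom row as the MedDRA preferred term of each qualifying event;
- count each patient once per preferred term per infusion;
- leave the total row and its one-IRR-per-infusion rule as they are;
- redraw the mock-up so that its rows agree with the header "Preferred Term/ Symptom of IRR";
- move the verbatim text to a listing that shows reported term and preferred term side by side.

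The cost is one specification line, a revised shell and a listing. The coding already exists, and no new data are needed.
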